11.1 Sample size

This study is predicated on an already established cohort with a fixed sample size from the original ACHIEVE trial (N=490 for the clinic-based hearing intervention cohort). In order to estimate the minimal difference in hours of continued hearing aid use that could be detected between the telehealth and conventional HHC groups after 12 months, we've made conservative assumptions based on expected loss to follow-up over time that would diminish the sample size and any observable outcomes. The initial cohort receiving the hearing intervention was N=490. Assuming conservatively that 5% of participants per year in this cohort are lost to follow-up or death, we would have a potential cohort of N=420 participants who would be eligible to participate after 3 years of follow-up from 2021-2022. If we further assume that up to 5% of these participants may then decline additional follow-up, we conservatively estimate that N=400 participants currently in the hearing intervention group will be recruited into this follow-up study (ACHIEVE-HIFU). Further conservatively assuming: 1) 10-20% loss to follow-up in the 12-month follow-up data collection; 2) 80% power and a 5% Type 1 error rate; and 3) that patterns of hearing aid utilization will be similar to those observed in the ACHIEVE pilot study, we would have the ability to detect an average treatment effect of 0.8 to 0.9 hours of hearing aid use between the telehealth HHC and conventional HHC arms.

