The Aging & Cognitive Health Evaluation in Elders (ACHIEVE) Hearing Intervention Follow-Up (HIFU) study is a randomized controlled trial nested within the ACHIEVE trial. Approximately 340 of the 490 participants in the hearing intervention group from the parent ACHIEVE study will be randomized to one of two conditions—telehealth Hearing Health Care (HHC) or conventional HHC. ACHIEVE-HIFU participants will be community-dwelling adults that were assigned to the hearing intervention arm of ACHIEVE, completed their final ACHIEVE Year 3 visit, and are willing and able to participate in two additional years of follow-up.

2. Background

Age-related hearing loss in older adults is a chronic health condition, according to the World Health Organization [1] [2] [3]. Current rates of hearing aid use among older adults with hearing loss in the U.S. are <20%, and rates of discontinuation of hearing aid use among older adults are estimated to be >30% [4] [5] [6] [7]. The clinic-based HHC model may be a contributor to low hearing aid utilization rates [8] [9] [10] [11]. Telehealth delivery of HHC is a form of remote service delivery that allows patients to access health care services from home via smartphones, tablets, and computers. Telehealth can be used to deliver services to adults with hearing loss including ongoing self-management support [12].

3. Objectives

The primary aim of ACHIEVE-HIFU is to compare the effect of telehealth HHC vs conventional HHC on hours of hearing aid use at one-year post-randomization. A secondary aim is to examine the effects of telehealth HHC vs conventional HHC on patient-centered hearing and communication outcomes. Exploratory analyses include (1) subgroup analyses of the primary and secondary outcomes, (2) differences in the utilization of hearing services, (3) quantifying the dose-response relationship between utilization of hearing services and hours of hearing aid use, and (4) assessing trends over time from randomization to the two-year follow-up.

4. Study Design

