ACHIEVE-HIFU is a randomized trial with two treatment arms: telehealth HHC and conventional HHC. Both treatment arms will receive the same clinic-based hearing intervention provided in the parent ACHIEVE study. However, participants assigned to the telehealth HHC treatment arm will be granted immediate access to HHC services via telehealth. Participants assigned to the conventional HHC treatment arm will be given access to the same telehealth services one year after randomization.

To be eligible for ACHIEVE-HIFU, participants must (1) have been eligible for and participated in the hearing intervention arm of ACHIEVE, (2) complied with ACHIEVE protocols, (3) be willing to be randomized to the telehealth HHC or conventional HHC treatment arm, and (4) be willing and able to complete two years of follow-up. The inclusion criteria for ACHIEVE were (1) 70 to 84 years old, (2) adult-onset bilateral hearing loss with a better-ear 4-frequency (0.5 to 4 kHz) pure tone average ≥ 30 and <70 dB, (3) free of substantial cognitive impairment (Mini-Mental State Exam ≥ 23 for high school degree or less; ≥ 25 for some college or more), (4) word recognition score in quiet $\geq 60\%$ correct in the better-hearing ear, community-dwelling, and (5) being a fluent English speaker. The exclusion criteria for ACHIEVE were (1) self-reported disability in ≥ 2 activities of daily living, (2) vision impairment worse than 20/63 on the MNREAD acuity chart (Precision Vision, Woodstock, IL) while using glasses or other reading aids typically used at home (corresponding to inability to comfortably read 14-point font), (3) self-reported hearing aid use in the past year, (4) permanent conductive hearing loss, (5) medical contraindication to hearing aid use, or (6) unwillingness to wear hearing aids on a regular basis.

Randomization for ACHIEVE-HIFU occurred up to 9 months after the participant's ACHIEVE Year 3 visit except at the University of Minnesota where delayed Institutional Review Board approval caused some participants to be randomized after more than 9 months. Spouse pairs were randomized to the same treatment arm. Participants will be followed for two years, with ACHIEVE Year 3 visit serving as the baseline.

5. Power

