ACHIEVE-HIFU is predicated on a finite sample of participants recruited from the treatment arm of the parent ACHIEVE study. An estimated 340 participants will be randomized to telehealth HHC or conventional HHC. Assuming conservatively that 5% of participants are lost to follow-up or death each year, we would have a sample of N=322 participants one-year post-randomization. With 80% power and a 5% Type 1 error rate, this sample would have the ability to detect an average treatment effect of 1.5 hours of hearing aid use between the telehealth HHC and conventional HHC arms.

6. Analysis Populations

Analyses will follow the intention-to-treat (ITT) principle in which participants will be analyzed in the condition to which they were randomized, regardless of whether they received the assigned intervention. Primary analyses will be based on the ITT population, which includes all randomized participants.

7. Statistical Analysis

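### Protocol 11.1 and SAP 5 give incompatible detectable differences (0.8 to 0.9 h versus 1.5 h) for the same primary comparison at the same analysed sample size

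*Protocol*

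**What the plan says.** Protocol section 11.1 starts from the 490 participants in the parent trial's hearing intervention arm and arrives at 400 recruited. It then assumes "10-20% loss to follow-up in the 12-month follow-up data collection", 80% power, a 5% type 1 error rate, and that "patterns of hearing aid utilization will be similar to those observed in the ACHIEVE pilot study". On that basis, "we would have the ability to detect an average treatment effect of 0.8 to 0.9 hours of hearing aid use". No SD is printed. Sections 2.1 and 5 repeat the estimate of 400.

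SAP section 5 says: "An estimated 340 participants will be randomized to telehealth HHC or conventional HHC". With 5% annual loss, "we would have a sample of N=322 participants one-year post-randomization", and at the same power and error rate "this sample would have the ability to detect an average treatment effect of 1.5 hours of hearing aid use". It gives no SD and no source. The SAP introduction also uses the lower recruitment estimate: "Approximately 340 of the 490 participants in the hearing intervention group from the parent ACHIEVE study will be randomized".

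Both power statements concern average daily hours of hearing aid use at one year, telehealth against conventional care, allocated 1:1.

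**The concern.** The two documents describe the same comparison, at the same power and error rate, on practically the same number of analysed participants, yet one detectable difference is 1.7 to 1.9 times the other (1.5/0.9 to 1.5/0.8). The text gives no means of telling which figure applies.

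Because the cohort is fixed, the detectable difference did not set the sample size; it is the only thing the power section delivers. No interim efficacy or futility analysis is planned (protocol 10.1), so estimation, inference and conduct do not depend on it. The exposure comes at reporting. A null result, or an observed difference near 1 hour, would be read against a trial said to detect under 1 hour by one document and only 1.5 hours by the other.

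**Working it through.** **Inputs.** Protocol 11.1: 400 recruited, 10-20% loss, 0.8 to 0.9 h. SAP 5: 340 randomised, 322 at one year, 1.5 h. Both: 80% power, 5% type 1 error. Sidedness is not stated; two-sided is assumed first.

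**Headcounts.** 490 × 0.95³ = 420; 420 × 0.95 = 399 (stated 400); 400 × 0.90 = 360 and 400 × 0.80 = 320 (derived, not printed in the protocol); 340 × 0.95 = 323 (stated 322). These hold up, and 322 falls inside 320-360.

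**Formula.** For an unadjusted, unweighted 1:1 comparison of means with total analysed N, detectable difference = (1.960 + 0.842) × SD × √(4/N). Neither stated difference can be reproduced directly, because no SD is given. Inverting for the SD each one implies:

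| Source | Difference | N | Implied SD |
|---|---|---|---|
| Protocol, 10% loss | 0.8 h | 360 | 2.71 h |
| Protocol, 20% loss | 0.9 h | 320 | 2.87 h |
| SAP | 1.5 h | 322 | 4.80 h |

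The variance ratio is (4.80/2.71)² = 3.14 to (4.80/2.87)² = 2.80.

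**Rounding.** A single SD of about 2.71-2.88 h gives both 0.8 and 0.9 after rounding; 1.5 needs about 4.64-4.96 h. The ranges do not overlap.

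**Exchanging the inputs.**
- Protocol SDs at N = 322: 0.85-0.90 h, not 1.5 h.
- SAP SD at N = 360 and 320: 1.42 and 1.50 h, not 0.8 and 0.9 h.
- N at which 1.5 h would be the protocol-basis figure: 360 × (0.8/1.5)² = 102 to 320 × (0.9/1.5)² = 115.

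**Other single explanations.**
- Protocol figure one-sided, SAP two-sided: the protocol-basis figure at N = 322 becomes 0.95-1.01 h.
- 90% instead of 80% power, upper protocol SD: 1.04 h at N = 322.
- Total N misread as per-arm N, SAP SD: 1.00-1.06 h at the protocol's sample sizes.
- Spouse pairs: the largest possible design effect is 2 (everyone paired, intraclass correlation 1), below the 2.8-3.1 needed.
- Baseline adjustment in the protocol figure only: needs R = √(1 − (2.71/4.80)²) = 0.83, or 0.80 from 2.87 h (R² 0.64-0.68).

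**Combinations (assumed values, not document figures).** A one-sided protocol figure alone leaves a variance ratio of 2.5-2.2. Adding a variance inflation of 1.2 to the SAP figure leaves 2.1-1.8; an inflation of 1.5 leaves 1.7-1.5. Sidedness and inflation of this size narrow the gap without closing it. A further R of 0.72-0.67 or 0.63-0.56 respectively would close it.

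**Consequences on each basis (same unadjusted two-sided test).**
- SD 4.80 h: power is 35% (0.8 h, N = 360) to 39% (0.9 h, N = 320). For 80% power, the analysed N would be 322 × (1.5/0.8)² = 1,132 or 322 × (1.5/0.9)² = 894, against a cohort of 490.
- SD 2.71-2.87 h: power for 1.5 h at N = 322 is above 99%.

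**The case against.** No arithmetic slip is demonstrated. Each figure follows from some SD, and two innocent explanations are available.

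First, the SAP may have replaced the pilot variability with later data. Only the protocol cites the pilot, and SAP section 4 describes randomisation as already past ("Randomization for ACHIEVE-HIFU occurred up to 9 months after the" Year 3 visit). Second, the protocol figure may be baseline-adjusted and the SAP figure not. Protocol 2.1 and 11.2 say that a list of variables, including logged baseline hours of use, will be considered as covariates in every model. SAP 7.3 lists the same variables without that sentence and keeps only the conditional wording that adjustment may follow an imbalance, which protocol 11.2 also contains.

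Both explanations are possible, and neither is documented: no power statement mentions adjustment, an assumed correlation or an updated SD. The later document cannot simply be taken to govern either, because protocol 11.2 describes the analysis plan as finalised while 11.1 still carries 0.8 to 0.9 h. In the text available for this review, which lacks the opening pages of both documents, neither marks the other's figure as superseded.

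It is also fair to say that the 35-39% power and the 894-1,132 participants are not the power of the planned weighted regression. They show how far apart the two statements are on a common basis. The limited harm stands too: this affects reporting and interpretation, not conduct. The difference between 400 and 340 is secondary, since both are labelled estimates and the differing loss assumptions largely cancel it.

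**Conclusion.** The concern holds. At essentially the same analysed N, power and error rate, no single SD and analysis basis yields both 0.8-0.9 h and 1.5 h. The implied SDs differ by a factor of 1.67-1.77 (variance ratio 2.8-3.1) on an unadjusted, unweighted, two-sided comparison. Sample size and rounding do not account for this, nor does sidedness alone. At least one figure is wrong, outdated or on a different, unlabelled basis; the documents do not show which. The implied SDs are back-calculated and are not values the documents state.

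**What to change.** Use one calculation in both power sections (protocol 11.1 and SAP 5), and align the recruitment estimate in protocol 2.1 and 5 and in the SAP introduction. State:

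- one randomised N, one 12-month loss assumption and the resulting analysed N;
- 5% type 1 error, explicitly two-sided, and 80% power;
- the SD, its source, and whether it is raw or residual after baseline adjustment, matching the primary model;
- the detectable difference that follows.

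For orientation at 322 analysed, an SD of 2.7-2.9 h gives 0.85-0.90 h and an SD of 4.8 h gives 1.5 h. If the SAP replaced the pilot SD, say so and retire the protocol figure. If both figures are intended, label them adjusted and unadjusted and give the assumed R.

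The cost is wording only, with no added participants or visits. The stated sensitivity in one document may become less or more favourable than it now reads.

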11.2 Analytic approach

The final statistical analysis plan was finalized in discussions between the study investigators and coordinating center.

The comparison for all primary analyses is randomization to the telehealth HHC vs. conventional clinic-based HHC delivery model under the intention-to-treat paradigm, analyzing individuals according to their random allocation, irrespective of the treatment received.

Consistent with best practices in clinical trials, we will assess the comparability of the randomized groups with respect to known confounders, such as recruitment source, site, level of hearing impairment, Quick Speech in Noise score, self-reported acceptance of telehealth at baseline, self-reported and objectively measured baseline hours of hearing aid use, self-reported baseline hours of hearing assistive technologies use, the number of days hearing log data was measured prior to randomization, and the number of visits prior to randomization at which a participant provided hearing logging data.⁴⁸ These variables will be considered as covariates in all models. If there is an imbalance between randomized treatment assignment, we may adjust for relevant confounders as well as explore the use of a prespecified inverse probability of treatment weight or a precise, locally efficient, augmented, simple estimator.^{49,50} A logistic regression model will be used to model the probability of attrition according to the confounders described above plus age, sex, and applicable interactions. Inverse probability of attrition weights will be calculated and either included in the model for the primary outcome directly or cross-multiplied with inverse probability of treatment weights.

We will use a weighted regression model with an identity link to compare average daily hours of hearing aid use at 1-year post-randomization between participants assigned to the telehealth HHC or conventional HHC. To account for the non-normal distribution of the outcome, confidence intervals and p-values will be obtained using the bias corrected and accelerated bootstrap resampling procedure with 10,000 replicates.

For continuous secondary outcomes, groups will be compared for differences at the 1-year follow-up using the same analytic approach specified for the primary outcome. For binary secondary outcomes, either logistic regression or Poisson regression with robust error variance will be employed, depending on whether the outcome is rare or common. For categorical outcomes, either ordinal or multinomial logistic regression models will be utilized, depending on the nature of the measure and empirical tests of the proportional odds assumption.

Statistical significance for the primary outcome will be defined as p < 0.05. Secondary outcomes will be evaluated for statistical significance with a Hochberg modification to the Bonferroni adjustment, in which the p-values of the five outcomes will be ordered. The largest p-value will be compared relative to p < 0.05, and if met, all parameters will be considered significant. If not, then the second largest p-value will be assessed relative to p < 0.05/2 = 0.025, and if met, then it and all other parameters will be considered significant, and so on for the third p-value at p < 0.05/3 = 0.017.

12 Data management

Trained data management and study management staff at the UNC CSCC will be responsible for coordinating data management. The Coordinating Center (CC) uses a customized state-of-the-art web-based data management system using Carolina Data Acquisition and Reporting Tool (CDART) which is also used for the parent ACHIEVE study and ARIC-NCS. A complete description of all data management procedures has previously been developed for the parent ACHIEVE trial and has been approved by the ACHIEVE DSMB. CDART uses a flexible, secure authentication system requiring a username and password. In accordance with HIPAA, all individually identifiable information is encrypted and decrypted for local on-screen display at field sites. The GrandPad tablet is HIPAA-compliant with respect to any telehealth sessions that occur using this platform.

Data collection

The CC has previously led the translation of the protocol data collection specifications into a consolidated set of clear, unambiguous electronic case report forms (eCRFs) for the parent ACHIEVE trial. Each eCRF has a corresponding paper form to be used by sites in cases where data cannot be entered at the time of collection.

Randomization and blinding

Randomization will be implemented within CDART. Although the ACHIEVE hearing interventions are by nature unmasked, in order to minimize bias based on review of accumulating data by the project team, the ACHIEVE PIs, co-investigators, and key project staff (except one unblinded statistician) will remain blinded to accumulating data. In all cases, hours of hearing aid use (primary outcome), a completely objective data point, will be gathered directly from hearing aid data logging software, and source data will be verified as part of the quality assurance procedures. All other non-audiological secondary outcomes will be collected by trained technicians, rather than the site audiologist.

Data quality control and monitoring

Quality and completeness of recorded data will be assured on an ongoing basis by range and logic checks upon entry, queries for missing or inconsistent data, and periodic monitoring. Consistent with the parent ACHIEVE trial a Quality Control Subcommittee chaired by MPI [name] meets monthly to review all data collection procedures and summary data tables to ensure the integrity of data collection and to troubleshoot as needed.

Records retention

MPIs and field center PIs will retain study essential documents and specimens for up to 10 years following study completion.

Ethical considerations

This study is to be conducted according to US and international standards of Good Clinical Practice (FDA Title 21 part 312 and International Conference on Harmonization guidelines), applicable government regulations and institutional research policies and procedures.

This protocol and any amendments will be submitted to a properly constituted single Institutional Review Board (sIRB), in agreement with local legal prescriptions, for formal approval of the study conduct. The decision of the sIRB concerning the conduct of the study will be made in writing to the investigator and a copy of this decision will be provided to the sponsor before commencement of this study.

All subjects for this study will be provided a consent form describing this study and providing sufficient information for subjects to make an informed decision about their participation in this study. This consent form will be submitted with the protocol for review and approval by the sIRB for the study. The formal consent of a subject, using the IRB-approved consent form, will be obtained before that subject undergoes any study procedure. The subject will sign the consent form, as will the investigator-designated research professional obtaining the consents.

13 Study sites and structure of the study team

13.2 Coordinating Center (CC)

The CC is located at the University of North Carolina (UNC). UNC currently serves as the CC for the ACHIEVE trial and ACHIEVE-MRI study and has served as the CC for numerous other studies, including ARIC. The CC will be responsible for programming data entry screens into the data management system, providing reports on study progress and data quality, creating datasets for sharing with investigators, and participating on study committees. See section 12 Data management for details on the data management system and data monitoring. See section 10.2 Adverse events for details on reporting of adverse events and unanticipated problems.

In addition to data management, the CC manages a centralized study-specific website, where study staff can login with their assigned individual user ID and password to access the latest version of the protocol, manuals of procedures, paper case report forms, current and prior IRB approval letters for each participating site, memos, and other relevant study documents. The website also has a directory feature that maintains contact information for all investigators and study team members at each participating site. The CC is responsible for distributing memos to the site PIs and/or study coordinators when there are changes to the protocol or clarifications to study procedures.

13.3 Hearing intervention unit

The University of South Florida (USF) will be responsible for training and oversight of the fidelity of the hearing intervention. USF will participate on study committees and lead the hearing intervention subcommittee.

13.4 Analysis and study governance site

Johns Hopkins University (JHU) is the analysis and study governance site. JHU will be responsible for overall trial coordination, leading several of the committees (described in the next section). JHU will be responsible for preparing and maintaining the study protocol, consent, and other study documentation, and will work with the CC to have these study documents distributed and/or posted to the study website as needed. JHU will also be responsible for preparing NIH progress reports.

